 271 also summarizes the flow of the Genetic Screening Phase. More detailed procedures are
 272 specified in the Pro-EYS Procedures Manual.

- 273 ➤ All genetic reports noted below to be uploaded to the study website by the clinical site or
 274 Central Lab may be available to and reviewed by the CC, associated clinical site, Central
 275 Lab, CGA, Genetics Committee, and investigators involved in oversight of the study
 276 (which include the study chair, Operations Committee, and FFB Consortium Executive
 277 Committee). All reports will be de-identified prior to uploading

278

279 Screening Group A

- 280 • The clinical site will upload supporting genetic documentation (including genetic reports)
 281 onto the study website
- 282 • A CGA will review the genetic documentation provided by the clinical site to verify the
 283 genetic screening data entry and appropriate documentation of the **final study cohort**
 284 **criteria** (section 2.5) of **at least 2 disease-causing variants** in the *EYS* gene which are
 285 **homozygous or heterozygous in trans**. Additional documentation may be requested as
 286 needed to verify the **final study cohort criteria** and all genetic screening assessments
 - 287 ○ If **final study cohort criteria** are verified, participant will be considered **enrolled**
 288 **into the study cohort**
 - 289 ○ Otherwise the participant will be a **genetic screen failure** (section 2.4.1)

290

291 Screening Group B or C

- 292 • The clinical site will upload supporting genetic documentation (including genetic reports)
 293 onto the study website
- 294 • Participants will be asked to provide a saliva sample, and approach at least 1 first-degree
 295 relative to provide a saliva sample for additional genetic testing. The first-degree
 296 relative(s) will be provided with information on how to provide informed consent and
 297 how to complete the saliva kit.
- 298 • The participant’s and first degree relative(s)’s samples will be shipped to and analyzed by
 299 the Central Lab to conduct retinal dystrophy panel genetic testing and determine the
 300 presence and number of disease-causing variants on the *EYS* gene (Screening Group B
 301 only), and the phase of the alleles from the family member testing (Screening Groups B

302 and C). The Central Lab will provide these assessments and its genetic report(s), which
 303 will be uploaded to the study website

304 ○ If the Central Lab determines there are at least 2 disease-causing variants in the
 305 *EYS* gene which are homozygous or heterozygous *in trans*, the participant's
 306 reports will move forward to CGA review

307 ○ Otherwise the participant will be a **genetic screen failure** (section 2.4.1)

308 ● A CGA will review the reports provided by the clinical site and the Central Lab to verify
 309 the genetic screening data entry and appropriate documentation of the **final study cohort**
 310 **criteria** (section 2.5) of **at least 2 disease-causing variants** in the *EYS* gene which are
 311 **homozygous or heterozygous in trans**. Additional documentation may be requested as
 312 needed to verify the **final study cohort criteria** and all genetic screening assessments

313 ○ If **final study cohort criteria** are verified, the participant will be considered
 314 **enrolled into the study cohort**

315 ○ Otherwise the participant will be a **genetic screen failure** (section 2.4.1)

316

317 **2.4.1 Genetic Screen Failures**

318 Participants who do not meet criteria to continue as noted above will be discontinued as a **genetic**
 319 **screen failure**. A Final Status Form will be completed, and the reason for screen failure will be
 320 noted.

321 **2.4.2 Genetics Committee Review**

322 A Genetics Committee will review the genetic documentation of participants with verified **final**
 323 **study cohort criteria** and **enrolled into the study cohort** for interpretation/evaluation of whether
 324 or not the *EYS* mutations are causative of the disease (i.e., pathogenic). Details of the process are
 325 described in the Pro-EYS Monitoring Plan. Cases that are not confirmed as disease- causing will
 326 remain in the study and will not be considered ineligible, however their data may be analyzed
 327 separately from those with pathogenic mutations.

328 **2.5 Participants Enrolled into the Natural History Study**

329 All participants meeting initial screening and eligibility criteria (section 2.3.1) who complete the
 330 Genetic Screening Phase (section 2.4) and meet the **final study cohort criteria** (defined below)
 331 will be considered **enrolled into the study cohort** and will complete the natural history study.

332 ➤ **Final Study Cohort Criteria:** At least 2 disease-causing variants in the *EYS* gene which
 333 are **homozygous or heterozygous in trans**, based on a report from a clinically-certified
 334 lab (or a report from a research lab that has been pre-approved by the study genetics
 335 committee), and confirmed by a CGA.

336

337

Chapter 3: Natural History Study Procedures

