- 86 • Use of standard, consistent definitions of pre-existing medical conditions, medications
87 and treatments, and adverse events (AEs) across all clinical sites
- 88 • A consistent schedule of follow-up visits for all participants with established visit time
89 frames
- 90 • A coordinating center (CC) is responsible for monitoring the conduct of the study to
91 ensure adherence to protocol

92

Chapter 2: Study Enrollment and Screening Visit

93 2.1 Participant Recruitment and Enrollment

94 Study participants will be recruited from approximately 30 clinical sites worldwide. All eligible
 95 participants will be included without regard to gender, race, or ethnicity. Potential eligibility will
 96 be assessed during a routine examination by an investigator prior to obtaining informed consent,
 97 as part of usual care, through referrals from other providers or self-referral.

98 2.1.1 Participant Recruitment Goals and Strategy

Recruitment will be tracked within 3 Vision Cohorts defined as follows. Sample size rationale is detailed in section 6.1.

- **Vision Cohort 1:** ~70 participants with the *better eye* Screening Visit visual acuity ETDRS letter score of 54 or more [approximate Snellen equivalent 20/80 or better] **and visual field** diameter 10 degrees or more in every meridian of the central field
- **Vision Cohort 2:** ~20 participants with the *better eye* Screening Visit visual acuity ETDRS letter score of 19-53 [approximate Snellen equivalent 20/100 - 20/400] **or** (visual acuity ETDRS letter score of 54 or more [approximate Snellen equivalent 20/80 or better] **and visual field** diameter less than 10 degrees in any meridian of the central field)
- **Vision Cohort 3:** ~10 participants with the *better eye* Screening Visit visual acuity ETDRS letter score of 18 or less [approximate Snellen equivalent 20/500 or worse]

The *better eye* is defined as the eye with better Screening Visit ETDRS VA. If both eyes have the same VA (defined as the same Snellen equivalent), then the determination will be made at investigator discretion as the eye with better fixation or clear ocular media to permit highest quality retinal imaging.

The *visual field* (VF) is defined as the clinically determined kinetic VF III4e performed within the last 18 months prior to or including the Screening Visit date.

	VF diameter ≥10° in every meridian	VF diameter <10° in any meridian
20/80 or better	Vision Cohort 1	Vision Cohort 2

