0.1	1.82
0.2	1.67

0.3	1.54
0.4	1.43
0.5	1.33
0.6	1.25
0.7	1.18
0.8	1.11
0.9	1.05
1.0	1.00

688

689 One objective is to estimate the correlation between eyes for the outcome measures; therefore,
 690 the value of the correlation is not known at the time of study design. We assume here a
 691 correlation of 0.8. This assumption is conservative in that it requires a higher number of
 692 participants than other plausible values of r.

693 The primary way sample size is evaluated is by considering the precision around the point
 694 estimates for the outcome measures of interest. Table 1 (including the table of specific values
 695 corresponding to the graph) provides the half width of the 95% confidence interval (CI) for the
 696 estimated mean percent change for combinations of the standard deviation (SD) of the
 697 distribution of percent change and sample size. The larger the SD, the wider the CI, meaning the
 698 range of possible true values grows.

699

700 **Table 1. Sample size versus half width of 95% confidence interval for the mean percent**
 701 **change for varying standard deviation values**

	Effective Sample Size (N of participants)				
	n=55 (50)	n= 72 (65)	n= 88 (80)	n= 99 (90)	n=110 (100)
SD=20%	5%	5%	4%	4%	4%
SD=30%	8%	7%	6%	6%	6%
SD=40%	11%	9%	8%	8%	7%
SD=50%	13%	12%	10%	10%	9%

702

[figure not shown]
703 **6.1.2 Sample Size Considerations for Comparing Percent Change from Baseline to 4 Years**
 704 **within Subgroups of Interest (All Outcomes)**

705 Another important objective for this natural history study will be to evaluate the association of
 706 possible risk factors with progression of various functional outcome variables (objective 3).
 707 Thus, it will be important to have a large enough total sample size to plan reasonable
 708 comparisons between subgroups. Figure 1 considers various expected SDs and evaluates the

709 power to detect varying differences in average percent change from baseline to 4 years,
 710 comparing subgroups of various equally distributed sizes. If subgroups are not equally sized the
 711 detectable difference (with the same power) will be larger.

712 Note: *within* subgroup point estimates and CIs will also be important. Table 1 above can be
 713 applied to potential subgroup sample sizes as well to consider the precision that would be
 714 observed.

715 **Figure 1. Power to conclude there is a difference given varying true difference values,**

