- 745 • Natural history of 12 participants with *EYS* mutations (Miyata/Yoshimura, 2016)
- 746 ○ -5.2 ±3.1% for IS/OS extent

747 **Assumptions made:**

- 748 • Expect average annual decline in *EYS* to be 6.25% per year or 25% by 4 years
- 749 • True SD of percent change at 4 years similar to VPA 1-year SD of around 20%

750 **Based on these assumptions and the impact as presented above, a sample size for the**
 751 **combined Vision Cohorts 1 and 2 of 90 patients or 99 effective eyes has been selected.** With
 752 an effective sample size of 99, the half width of a 95% CI around the point estimate for percent
 753 change would be 4%. A comparison of two equal-sized subgroups would have about 80% power
 754 to conclude there is a difference if the true difference is 11%.

755 Based on the above justification, the total sample size will be 100 participants enrolled.
 756 Recruitment is anticipated to take 10 months from the time of study launch.

757 **6.1.4.1 Synopsis of Justification for All Outcomes**

758 The primary objective of the study is to characterize the natural history of retinal degeneration
 759 using the main outcome measures. Therefore, the precision of these estimates (how tight the CI
 760 is around the point estimate) for all of the outcomes of interest will be of the greatest importance
 761 in the consideration of sample size. With a sample size of 90 participants (effective sample size
 762 N= 99) for Vision Cohorts 1 and 2, all of these outcomes will have 95% CIs no wider than +/-
 763 4% (when analyzed in terms of percent change from baseline) if the SD is within 20%. Based on
 764 the available data, we expect the SD to be within 20%, which would yield CIs no wider than +/-
 765 4%. With an even smaller sample size of 65 participants (effective sample size N= 72), all of
 766 these outcomes will have 95% CIs no wider than +/- 5% if the SD is within 20%. This was
 767 considered acceptable precision to meet our objective for all outcomes of interest.

768 Furthermore, for the additional objective of evaluating risk factors associated with progression of
 769 these outcomes, a sample size of 90 (effective sample size N= 99) participants for Vision Cohorts
 770 1 and 2 will provide enough power to evaluate subgroups, especially those with close to equal
 771 distribution. For example, for 2 subgroups of equal size there will be at least 69% power to

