 772 detect differences as small as 10% if SD is within 20%. With a sample size of 65 (effective
 773 sample size N= 72), there will be at least 55% power to detect differences as small as 10% if SD
 774 is within 20%.

775 For objective 4 of evaluating variability and symmetry, a sample size of 90 participants for
 776 Vision Cohorts 1 and 2 will have a 95% CI of (0.34, 0.63) when observed r equals to 0.5, and
 777 (0.72, 0.86) when observed r equals to 0.8. With a smaller sample size of 65 participants, the
 778 95% CI would be (0.30, 0.66) when observed r equals to 0.5, and (0.70, 0.87) when observed r
 779 equals to 0.8. This is considered acceptable precision to meet our objective.

780 **6.2 Data Analysis**

781 The analysis plans below are written with respect to the majority of outcomes of interest.
 782 Analyses will include data on both eyes for each participant, and models and confidence
 783 intervals will adjust for correlation between 2 eyes of the same participant.

784 **6.2.1 Primary Objectives Analyses**

785 The primary objectives of the natural history study and brief analysis plan for each are as
 786 follows.

- 787 1. Characterize the natural history of retinal degeneration associated with biallelic
 788 pathogenic mutations in the *EYS* gene over 4 years, as measured using functional,
 789 structural, and PRO measures
 - 790 a. Analysis plan for functional and structural measures: The distribution of each
 791 outcome at each visit will be summarized (including tabulating categorically, as
 792 well as means, SDs, medians, quartiles, ranges; both the absolute change and
 793 percent change will be evaluated, tests performed multiple times will be analyzed
 794 using average of all available tests). To determine the average annual rate of
 795 progression in the population for each outcome, a repeated measures least squares
 796 regression model will be fit using all available outcome data at baseline and all

797 annual visits. Multiple imputation will be used to impute the outcome values for
 798 all missing time points (including participants who discontinue follow up prior to
 799 48 months). Secondary analyses using binary definitions of outcome measures
 800 will also be explored in time to event analyses; Kaplan-Meier estimates with 95%
 801 confidence intervals will be calculated. Mixed effects linear models for the
 802 continuous outcome measures and for the time-to-event analyses will also be

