 834 analysis of covariance (ANCOVA) models (adjusting for baseline). A stepwise
 835 selection procedure will be used to build the final model. A threshold of $P < 0.10$
 836 will be used to add to the model, and a threshold of $P < 0.01$ will be used to remain
 837 in the multivariate model. Missing outcome data will be imputed using multiple
 838 imputation as noted in the primary analysis. Linearity of continuous factors will
 839 be assessed and possibly quadratic or cubic terms will be considered if non-linear.
 840 Secondary analyses using binary definitions of outcome measures will also be

- 841 explored in time to event analyses; Cox proportional hazard models will be
 842 evaluated using a parallel stepwise selection procedure.
- 843 • Potential risk factors to evaluate include:
 - 844 ○ Phenotypic:
 - 845 ▪ Clinical diagnosis
 - 846 ▪ Age of onset of initial vision symptoms
 - 847 ▪ Gender
 - 848 ▪ Race/ethnicity
 - 849 ▪ Visual acuity
 - 850 ▪ Lens Status (phakic/pseudophakic/aphakic)
 - 851 ▪ ERG 30 Hz flicker cone amplitudes b-wave (continuous)
 - 852 ▪ FAF pattern as measured qualitatively
 - 853
 - 854 ▪ SD-OCT (as factors related to SP Hill Of Vision (HOV))
 - 855 • Presence of cysts
 - 856 • Central subfield thickness
 - 857
 - 858 ▪ MP
 - 859 • Mean retinal sensitivity
 - 860
 - 861 ▪ SP (as factors related to SD-OCT EZ area)
 - 862 • Volume of 30 degrees HOV
 - 863 • Mean sensitivity
 - 864 • Full field HOV
 - 865 ○ Genotypic:
 - 866 ▪ Characterizations of the variants on the *EYS* protein
 - 867
 - 868 ○ Environmental factors
 - 869 ▪ Smoking status at baseline
 - 870 ▪ Vitamin A use at baseline
 - 871 ▪ Docosahexaenoic acid (DHA) use at baseline
 - 872 ▪ Lutein use at baseline
- 873 4. Evaluate variability of repeat perimetry testing and symmetry of left and right eye
 874 outcomes over 4 years in individuals with biallelic pathogenic mutations in the *EYS* gene
- 875 a. Analysis plan for variability of repeat perimetry testing at baseline: Scatterplots
 876 and Spearman correlation coefficients for pairs (first versus second) of testing
 877 values for each repeated perimetry test. Bland-Altman plots of the inter-eye
 878 difference versus the mean value will be inspected and a linear regression model
 879 for the differences will be used to test whether the slope is 0 and whether
 880 variability changes with greater mean values. The intraclass correlation

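### The stated analysis rule handles correlation between a participant's two eyes but no family level, and no family link is listed among the collected data; if affected siblings enrol, intervals are slightly too narrow and genotype tests too liberal

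*Protocol*

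**What the plan says.** - **Who can enrol.** Section 2.1: "Study participants will be recruited from approximately 30 clinical sites worldwide. All eligible", continuing "participants will be included without regard to gender, race, or ethnicity". Candidates are identified "as part of usual care, through referrals from other providers or self-referral". The participant and ocular criteria in sections 2.3.1.1 and 2.3.1.2 neither exclude a relative of someone already enrolled nor cap the number per family.
- **What the analysis adjusts for.** Section 6.2 says models and confidence "intervals will adjust for correlation between 2 eyes of the same participant". No level above the participant is named.
- **What the sample size discounts.** Section 6.1.1 multiplies participants by 2/(1+r) for the two eyes, with r = 0.8. Section 6.1.4 arrives at 90 participants or 99 effective eyes in Vision Cohorts 1 and 2. Section 6.1.4.1 concludes that "all of these outcomes will have 95% CIs no wider than" ±4% if the SD is within 20%.
- **Where genotype enters.** Section 6.2.1, objective 3, lists "Characterizations of the variants on the" EYS protein as a candidate risk factor, in a stepwise model with P<0.10 to enter and P<0.01 to stay.
- **What family information is collected.** The genetic assessment in section 2.3.2 covers number and phase of variants, consanguinity and the source reports. No link between related participants is listed. Reports are de-identified before upload (section 2.4), and contact details stay at the site (section 2.3.2).

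**The concern.** The cohort is defined by two disease-causing EYS variants in trans or homozygous, in a recessive disease. An affected full sibling of a participant will normally carry the same two variants and so meet the genetic criterion. Two such siblings are not two independent observations of the disease course if their progression is alike. An analysis that knows only about eyes within a person counts them as if they were.

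The effect on the average rate of progression is small for a modest number of siblings. It matters more for objective 3. Full siblings fall in the same variant class, so their shared course does not cancel in a comparison of classes. In a class fed by few families, one family's course can look like a genotype effect. Section 1.1 says genotype-phenotype relations are not strongly established, and the study aims to identify subpopulations for future trials, so such a result could be acted on.

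There is also a timing problem. The SAP can add a family term later, but only if someone has recorded who is related to whom.

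**Working it through.** **Inputs from the protocol:** 90 participants, r = 0.8, SD of 4-year percent change 20%, effective N 99, stay threshold P<0.01.

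**Inputs assumed, because the protocol gives none:** share s of participants who belong to an enrolled sibling pair, 0-30%; correlation ρ of 4-year change between siblings, 0.3-0.7.

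**Step 1: reproduce the plan's figures.**
- Effective N: 90 × 2/(1+0.8) = 100; with the multiplier rounded to 1.1, 90 × 1.1 = 99, as stated.
- Half width: t(0.975, 98) × 20/√99 = 3.99% (3.94% with 1.96). Stated: 4%.
- Power for two equal subgroups at effective N 99 (normal approximation, two-sided 0.05 assumed): 78.1% for a difference of 11% (stated: about 80%) and 70.1% for 10% (stated: at least 69%).

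**Step 2: variance inflation from sibling pairs.** Each of the sN participants in a pair has one partner with correlation ρ, so the variance of the mean is multiplied by VIF = 1 + sρ.
- s = 0: 1.00
- s = 0.10, ρ = 0.3: 1.03
- s = 0.30, ρ = 0.7: 1.21

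The same factor applies to a genotype contrast when pairs are spread evenly over the classes, because both siblings sit in the same class.

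**Step 3: half width and power.**
- Half width = 3.99% × √VIF: 3.99% at 1.00, 4.05% at 1.03, 4.39% at 1.21. At most the correct interval is √1.21 = 1.10 times as wide.
- At the permitted minimum of 65 participants (effective N 72): 4.70% at 1.00 and 4.70 × 1.10 = 5.17% at 1.21, against a stated 5%.
- At VIF 1.21, effective N is 99/1.21 = 81.8, and power for an 11% difference falls from 78.1% to 70.1%.

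**Step 4: real error rates if family is ignored.** Size = 2 × (1 − Φ(z/√VIF)).

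| VIF | coverage of a 95% interval | size of a 0.05 test | size of the 0.01 rule |
|---|---|---|---|
| 1.00 | 95.0% | 5.0% | 1.0% |
| 1.03 | 94.7% | 5.3% | 1.1% |
| 1.21 | 92.5% | 7.5% | 1.9% |

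These sizes are for a single test at the threshold. They do not include the effect of stepwise selection.

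**Step 5: a variant class where half the carriers are sibling pairs.** With s = 0.5 and ρ = 0.5-0.7, VIF is 1.25-1.35 and the 0.01 rule runs at 2.1-2.7%. This applies when that class supplies most of the variance of the contrast, as a small class set against a large remainder does.

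**Step 6: check by simulation** (8,000 runs, 90 participants, sibling pairs sharing genotype).
- s = 0.2, ρ = 0.5: coverage 94.2% and size 5.8%; formula 93.8% and 6.2%.
- s = 0.4, ρ = 0.5, beyond the assumed range: coverage 92.7% and size 7.2%; formula 92.6% and 7.4%.

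**The case against.** **This belongs in the SAP.** Chapter 6 calls itself a framework, and the sentence in section 6.2 does not say that eyes are the sole correlation to be handled. That stands as far as the model goes: a family term is not ruled out. It does not cover the data. Family membership has to be recorded during the study, and the protocol lists nothing that would do so. The procedures manuals and case report forms are not at hand and may contain it.

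**No relatives may enrol, or their courses may differ.** This stands. The protocol does not say that siblings will take part, and section 1.1 reports the same mutations giving different phenotypes. The point is therefore conditional, and zero belongs in the range.

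**The planned precision has slack.** Section 6.1.1 assumes a "correlation of 0.8. This assumption is conservative in that it requires a higher number of" participants than other plausible values. At r = 0.5 the effective N would be 90 × 1.33 = 120, and 120/1.21 = 99. Section 6.1.4.1 also accepts ±5%. This stands for planned width. It does not repair coverage or test size, because the final intervals will use the eye correlation seen in the data and would still ignore family.

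**Stronger readings that the protocol does not support.**
- A reader might infer from section 2.4 ("Participants will be asked to provide a saliva sample, and approach at least 1 first-degree" relative) that relatives are recruited. They give saliva to establish phase, in Screening Groups B and C only, under a separate consent for the sample (section 2.2).
- A reader might say that ±4% is breached. Table 1 is in whole percent, and 4.39% still rounds to 4%, as 5.17% rounds to 5%.
- Relatives do not always share a variant class. That is expected of full siblings, not of cousins or of parent and child.
- A site effect might seem to follow by the same logic. It is a separate question: the protocol gives no site correlation, and section 1.4 sets out standard procedures, staff certification and uniform Reading Center grading.

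**Conclusion.** The concern holds in conditional form. The protocol sets no per-family limit, names only between-eye correlation in both the sample size and the analysis, and lists no family link in its data. If affected full siblings enrol with positively correlated progression, the direction of the error is certain: intervals too narrow, genotype tests too liberal. The size rests on two assumed quantities. Over the assumed range the intervals should be at most 10% wider, which does not upset the sample size justification. The genotype tests carry the larger risk: up to nearly twice the nominal rate at the 0.01 threshold overall, and two to nearly three times in a variant class dominated by siblings. It would be wrong to conclude that the study's intervals and P-values are certain to be too small. This is an inexpensive improvement worth making while family membership can still be recorded, not a flaw that invalidates the design.

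**What to change.** 1. Add a de-identified family number to the enrolment form, shared by participants who are related.
2. In section 6.2, add that models and confidence intervals also account for participants of the same family if relatives are enrolled, by standard errors clustered on family (which also cover the two eyes) or a family random effect. With 10% of 90 participants in pairs there would be only four or five pairs, so a family variance may be poorly estimated. Clustered standard errors do not need it.
3. Repeat the genotype analyses of objective 3 with one participant per family, chosen by a rule fixed beforehand, such as the first enrolled. This matters most in small variant classes, where clustered standard errors rest on few families.

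The cost is one data field, a sentence in the protocol with matching SAP text, and slightly wider intervals if relatives enrol. If none do, results are essentially unchanged.
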